1 INTRODUCTION

This document is a clinical investigational plan for a human research study. The study will be conducted in accordance with the ethical principles that have their origin in the Declaration of Helsinki. By participating in the study, the Investigator agrees to adhere to all stipulations of this protocol, the conditions of IRB approval, federal and local regulatory requirements, 21 CFR 812, ISO-14155 and International Conference on Harmonization Good Clinical Practice guidance ICH GCP.

1.1 Background and Rationale

The aim of the current project is to investigate the effectiveness of Auricular Percutaneous Electrical Nerve Field Stimulation (PENFS) device in the management of post-operative pain following hip arthroplasty. In 2020, an estimated 498,000 primary total hip arthroplasties are expected to be performed in the US and forecast to grow by over 30% in the next 5 years driven by significant gains in quality of life post joint replacement, an aging population, and an obesity epidemic with increasing osteoarthritis (OA) incidences [1]. Despite the availability of non-opioid treatments for postoperative pain following THA, approximately 90% of patients were still prescribed opioids within 60 days from discharge [2]. Postoperative pain can have a negative effect on patient tolerance of rehabilitation exercises, which is important to help return to normal functioning. As compared to the present use of opioids for perioperative pain management, the use of a complementary, non-pharmacologic approach offers the advantage of analgesia without the associated side effect and eliminating the potential risk of opioid addiction stemming from exposure to the drug. If effective, this alternative approach may revolutionize post-operative pain management and have a substantial impact on health care costs and morbidity.

Masimo Corporation develops technologies that help reduce the risks associated with prescribed opioids, such as overdoses and opioid use disorder. In particular, opioid use disorder is a serious public health issue that negatively impacts many communities around the world, and the current opioid epidemic has led to a renewed interest in exploring non-pharmacological techniques to treat post-operative pain. In the United States, over \$600 billion is spent every year on opioid addiction, including \$79 billion related to opioid addiction following surgery. Furthermore, an increasing number of patients are suffering from other known adverse effects of opioid use following surgery, including post-operative nausea and vomiting, respiratory depression, immunosuppression, and constipation.

Despite many initiatives to decrease the use of opiates in the perioperative setting, opioids continue to be regularly prescribed before, during and after surgery. Although the risk of opioid addiction following surgery is recognized, the percentage of patients who develop an opioid use disorder following surgery is not well understood. To date, there has been virtually no agreement regarding the duration and dosage that qualify for opioid dependence following surgery, nor that a clear estimation of the factors such as biological, psychosocial and socioeconomic that increase the risk of using opioids for extended periods of time after surgery. Therefore, in order to combat this growing health crisis at the ground level, it is incumbent upon the medical community to explore alternative methods of pain control to treat the surgical population in order to change the incidence of post-operative opioid addiction.

Percutaneous Nerve Field Stimulation (PNFS) is one of these recognized methods that ongoing research has shown to be effective as a complementary method of pain management. While PNFS is not a novel concept, clinical indications of auricular field stimulation have been limited in the past due to requirement of bulky, stationary and non-disposable stimulators and electrodes. These technological limitations made it difficult to establish the real clinical potential of auricular stimulation for the perioperative management of pain in surgical patients, despite the demonstration that auriculotherapy has been shown to relieve pain in the postoperative setting.

Bridge™ is a battery operated and disposable Auricular Percutaneous Electrical Nerve Field Stimulation (PENFS) device that is FDA cleared for the treatment of symptoms related to opioid withdrawal, conditions that include pain and nausea and

vomiting, which also happen to occur in patients following surgery. Furthermore, preliminary data suggests that the Bridge device may be useful in controlling perioperative opioid consumption and pain following kidney donor surgery [3]. The novelty of the Bridge device is in its use of alternating currents of stimulation over a large field and with higher voltage in order to influence central pain areas. Specifically, the device stimulates branches of Cranial Nerves V, VII, IX and X, and the occipital nerves, identified by transillumination. Such stimulation is transmitted to the nucleus of these cranial nerves which interact with a number of other nucleus located at the level of the central nervous system, the limbic system, and the ascendant and descendant pain pathway. This allows the modulation of stress, anxiety and pain through the interaction, for example, of the nuclei of the amygdala (structure involved in the response to fear and anxiety), the thalamus (structure involved in the management of visceral and somatic pain, and addiction), and tractus solitarius (structure involved in the control of blood pressure). The stimulation of these nuclei produces a modulation of the pain impulses from the visceral and/or somatic structures to supraspinal areas; and a reduction in anxiety and control of blood pressure and heart rate associated with the sympathetic and parasympathetic nervous system.

2 STUDY DEVICES

[figure not shown]
2.1 Bridge (active) vs. Sham device

Bridge is a device that electrically stimulates branches of Cranial Nerves V, VII, IX and X, and the occipital nerves identified by transillumination through percutaneous electrodes.

The components of the Bridge device include the following:

- Percutaneous electrical nerve field stimulator (PENFS) system
- Multi-pin wire harness percutaneous electrode
- Pen light for use in the transillumination technique that aids in positioning of the percutaneous electrodes

The wire harness percutaneous electrode array consists of 4 leads. The 1-1-1-4 configuration consists of three single-needle leads, and one 4-needle array. The stimulator is placed behind the ear and percutaneous electrodes are positioned utilizing the transillumination function of the device. The transillumination technique assists in the visualization of neuro-vasculature matrixes, to aid in the placement of the percutaneous electrodes near the nerve branches in the ear. The Bridge device has a 120 hour run-time and has a pulse sequence of 2 hours on and 1 minute off with the cycle repeating over the 120 hour run-time.

The sham device has the same appearance and will require the same placement technique as the Bridge (active) device but will not deliver electrical impulses.

2.2 Device Accountability

2.2.1 Receipt of Study Devices

Masimo may ship or hand-carry devices and study supplies to the investigative site. Upon receipt of the of the study device and supplies, an inventory must be performed and the Equipment Shipment Check Form (FRM-2713) and the Device Accountability Log (FRM-3407) will be completed for each device and signed by the receiver. It is important that the designated study staff counts and verifies that the shipment contains all the items noted in the shipment inventory. Any damaged or unusable study devices in a given shipment will be documented in the study files. The investigator must notify the study sponsor of any damaged or unusable study devices that were supplied to the investigator's site.

2.2.2 Use of Study Device

Use of devices will be documented on case report forms (CRF) for each subject. Any unused devices must be returned to the Sponsor at the end of the study or before product expiration date.

2.2.3 Return or Destruction of Study Device

At the completion of the study, there will be a final reconciliation of study devices. This reconciliation will be logged on the device accountability log. Any discrepancies noted will be investigated, resolved, and documented prior to return or destruction of unused study devices. Devices destroyed on site will only be upon written instruction from the Sponsor and will be documented in the study files.

2.3 Risk/Benefits

Benefits: There may be direct benefits to the enrolled subjects. The Bridge device may be used as an aid to reduce post-operative pain symptoms if they receive the active device. There are no anticipated benefits to subjects who receive the sham device.

Device risks: The Bridge device is to be operated by, or under the supervision of, qualified personnel only. Read the manual, directions for use, all precautionary information, and specifications before use. Refer to the Operator's Manual for safety information, warnings, and cautions.

- The device is contraindicated for use by patients with cardiac pacemakers, hemophilia and psoriasis vulgaris.
- The device should only be applied to healthy, clean, intact skin.
- The device therapy is limited to 120 hours, after which the device is disposable.
- The appliance is splash-proof but not water tight. When showering, the device must not be allowed to come into direct contact with water.
- The device is also contraindicated for use in patients with a previous history of sensitivity to compound benzoin tincture, which is used to attach the electrodes to the ear.

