6.3 Exclusion Criteria

- Subjects with a PROMIS Anxiety raw score of >19
- Subjects who are pregnant or breastfeeding
- Subjects with cardiac pacemakers or other implanted devices (e.g. vagal nerve simulators)
- Subjects with hemophilia
- Subjects with Psoriasis vulgaris
- Subjects with a history of active depression, anxiety or catastrophizing
- Subjects with active alcoholism or drug abuse
- Subjects with severe chronic pain condition that requires daily preoperative opioid dependence
- Subjects deemed not suitable for the study at the discretion of the principal investigator
- Subjects who are concurrently participating in any other research study

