7 STUDY PROCEDURES

7.1 Subject Recruitment and Pre-Screening

Persons scheduled for elective total hip arthroplasty will be approached and screened by a Principal Investigator, nurse or research staff for suitability for this study. Persons who meet all of the inclusion and none of the exclusion criteria will be asked if they are interested in participating in the study. A subject is considered enrolled in the study once the subject's written informed consent has been documented. Consent may be obtained pre-surgery.

If the subject signs the Informed Consent form and is identified later as failing to meet all eligibility criteria, the subject will be classified as a screen failure. Upon determination that the subject does not meet all eligibility criteria, the reason for the subject's ineligibility will be documented on the Screening and Enrollment Log for the study. In the event that a subject leaves the study prematurely or is withdrawn from the study, another subject may be recruited.

A partial waiver of HIPAA authorization is being requested for the pre-screening process for this study. The pre-screening process would require study personnel to access personal health information to identify prospective subjects without HIPAA authorization, and this would occur prior to introducing them to the study or obtaining informed consent. Informed consent and HIPAA authorization will be obtained for all patients who are interested in participation; however, the pre-screening process would require a partial waiver of HIPAA authorization, as the research study could not be practically carried out without this partial waiver of authorization. The participants' rights and welfare are not adversely affected by the waiver. Patients' protected health information (PHI) will not be inappropriately reused or disclosed to any other person or entity. To further safeguard all protected health information, the data collected for the purposes of this study will not be labeled with any personal identifying information, or with a code that can be linked to personal identifying information. The data will not be stored with any protected health information identifiers.

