8.3 Definitions

The definitions for adverse event, adverse device effect, serious adverse event, serious adverse device effect, and unanticipated adverse device effect are provided below (ISO 14155:2011, 21 CFR 812.3(s)).

- Adverse Event (AE): an adverse event is any untoward medical occurrence in a subject which need not be related to the device under investigation.
- Adverse Device Effect (ADE): an adverse device effect is any untoward or unintended response to a medical device which may result from insufficiencies in the instructions for use or deployment of the device, or from use error.
- Serious Adverse Event (SAE): a serious adverse event is an adverse event that results in death, inpatient hospitalization, severe or permanent disability, a life threatening illness or injury, fetal distress, fetal death, a congenital abnormality, a birth defect, or medical or surgical intervention to prevent permanent impairment to body or structure.
- Serious Adverse Device Effect (SADE): a serious adverse device effect is an adverse device effect that results in death, inpatient hospitalization, severe or permanent disability or is life threatening.
- Unanticipated Adverse Device Effect (UADE): any serious adverse effect on health or safety or any life threatening problem or death caused by or associated with, a device, if the effect, problem, or death was not previously identified in nature, severity or degree of incidence in the investigational plan, or application (including a supplementary plan or application) or any other unanticipated serious problem associated with a device that is related to the rights, safety or welfare of subjects. Refer to the Device Risk Analysis and Risk Assessment section for details on anticipated adverse device effects.

8.4 Anticipated Adverse Events:

- Bleeding or infection at the puncture site
- Skin irritation
- Pain at the site of application
- Allergic contact dermatitis to the compound benzoin tincture.

8.5 Adverse Event Reporting:

- All Adverse Events, both Anticipated and Unanticipated, must be recorded within the CRF on the Adverse Event Report Form.
- All Adverse Events must be promptly reported to the Sponsor.
- All Unanticipated Adverse Device Effects will be also reported to both the Sponsor and the IRB.
- Both Serious Adverse Events and Unanticipated Adverse Device Effects must be reported to the Sponsor within 48 hours. All other Adverse Events should be reported to the Sponsor within 5 business days.

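### Benzoin tincture sensitivity is a contraindication in Section 2.3 but not an exclusion in Section 6.3, so a contraindicated subject can be enrolled and randomised

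*Combined protocol and SAP*

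**What the plan says.** Section 2.3 (Risk/Benefits) gives the contraindications in two separate bullets. The first reads "The device is contraindicated for use by patients with cardiac pacemakers, hemophilia and psoriasis vulgaris". The second, three bullets later, reads "The device is also contraindicated for use in patients with a previous history of sensitivity to compound benzoin tincture" and explains that the tincture is what fixes the electrodes to the ear.

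Section 6.3 (Exclusion Criteria) has a line for each condition in the first bullet, for example "Subjects with hemophilia" and "Subjects with Psoriasis vulgaris". No line names benzoin, allergy or adhesive sensitivity. The inclusion criteria in Section 6.2 do not mention it. Section 6.3 also lets the principal investigator exclude anyone judged unsuitable.

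Section 7.1 sets the rule for approaching people: "Persons who meet all of the inclusion and none of the exclusion criteria will be asked if they are interested in participating". Enrolment is defined there as documented written consent, and Section 7.3.4.1 places randomisation at enrolment.

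The tincture appears once more, in the anticipated adverse events of Section 8.4: "Allergic contact dermatitis to the compound benzoin tincture".

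**The concern.** The protocol's contraindication list and its eligibility list disagree. Screening staff work from Sections 6.2 and 6.3, and a person with a known benzoin reaction passes every specific line in both. Section 2.3 says that same person should not receive the device.

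Two things are at stake. The first is safety: a subject could be exposed to a substance to which a reaction is already on record. The second is the randomised comparison. If the sensitivity comes to light only when the device is about to be placed, the subject has already been allocated and becomes a loss that one screening question would have prevented. In a trial capped at 60, each such loss is at least 1/60 = 1.7% of the randomised subjects.

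**Working it through.** This is a check of text against text. The plan states no figure to reproduce.

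**Step 1. Match each contraindication in Section 2.3 to the criteria.**

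| Contraindication in 2.3 | Matching line in 6.3 |
|---|---|
| Cardiac pacemaker | Yes, widened to other implanted devices |
| Hemophilia | Yes: "Subjects with hemophilia" |
| Psoriasis vulgaris | Yes: "Subjects with Psoriasis vulgaris" |
| Previous sensitivity to compound benzoin tincture | None |

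Three of four are matched. Section 6.2 supplies nothing for the fourth.

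**Step 2. Look for another step that would catch it.**

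- Section 7.3.1 has staff verify eligibility before surgery, but against the same incomplete list. The medical history described there is something that may be captured, and allergy is not named.
- The discretion line in 6.3 permits exclusion. It does not require it and prompts nobody to ask.
- Section 2.3 refers users to the Operator's Manual, and Section 4.1.1 has the device attached according to its instructions for use. Both govern use of the device, not screening.
- Section 10.3 records the inclusion and exclusion criteria on the CRF, and Section 11.5 has the monitor verify adherence to them. A benzoin-sensitive subject breaches no specific criterion, so neither check would flag the case.

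**Step 3. Put the events in order.** Consent is enrolment (7.1). Randomisation is at enrolment (7.3.4.1). Surgery follows under spinal plus sedation (7.3.2). The device is then applied in the recovery unit (4.1.1). Any discovery at placement is therefore after randomisation.

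**Step 4. Illustrate the size.** The documents give no prevalence of benzoin sensitivity, so p below is assumed. The number 60 is the enrolment ceiling in Sections 4 and 6.1. The calculation supposes that no informal safeguard works.

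P(at least one) = 1 − (1 − p)^n, and the expected number is n × p.

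| Assumed p | n = 60 | Expected in 60 |
|---|---|---|
| 0.1% | 1 − 0.999^60 = 0.058 | 0.06 |
| 1% | 1 − 0.99^60 = 0.453 | 0.6 |
| 5% | 1 − 0.95^60 = 0.954 | 3 |

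The documents do not say whether the tincture is used on the sham. Section 2.1 gives the sham the same placement technique, while Section 4.1.2 says it has no electrode needles. If only the active arm received tincture, and allocation were 1:1 (also an assumption), n would be 30. The chance of at least one exposed subject at p = 1% would then be 1 − 0.99^30 = 0.260.

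**The case against.** The strongest reply is that Section 2.3 belongs to the same protocol and Section 1 binds the investigator to all of it. On that reading, applying the device to a subject known to be sensitive would breach the protocol, so actual exposure requires staff to overlook 2.3. The coordinators are trained, the instructions for use must be followed, and a stated contraindication is an obvious use of the discretion line. This lowers the likelihood of exposure. It does not remove the gap, because none of these provisions makes anyone ask about benzoin before allocation.

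A second reply is that much of the relevant procedure cannot be seen. Parts of Sections 7.3.3 to 7.3.5 are redacted, the schedule in Table 1 is not legible, and the eligibility CRF is not supplied. A check at placement may exist, and the CRF may already carry the item. That is fair. But a placement check would come after randomisation, and the list in Section 6.3 is fully visible and lacks the line.

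A third reply is that the probabilities simply follow whatever prevalence is chosen, that the sham arm may not be exposed, and that the only harm the documents name is contact dermatitis. This stands as a limit on emphasis. The figures are illustrative and the finding does not rest on them.

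Lastly, Section 7.1 allows another subject to be recruited when one leaves. Replacement restores the head count but not the original randomised comparison. It is true that no effect on sample size, power or type I error is shown.

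**Conclusion.** The concern holds. Section 2.3 contraindicates the device in a group that Section 6.3 does not exclude, and no visible text requires screening for it before randomisation. Under the eligibility rules as written, a contraindicated subject can be consented and randomised. Since three of the four contraindications were carried across and the one in a separate bullet was not, this looks like an oversight.

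It is an internal contradiction bearing on subject safety and should be corrected before enrolment proceeds. Its practical size is uncertain. Over assumed prevalences from 0.1% to 5%, the chance of at least one such subject among 60 runs from about 6% to 95%. The endpoints, sample size and analysis are unaffected. The conclusion rests on the visible criteria in Sections 6.2 and 6.3. A check hidden in redacted text could reduce exposure but would not correct the eligibility list.

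**What to change.** Reconcile Section 6.3 with Section 2.3 so that every contraindication stated in 2.3, including the benzoin tincture one, has a matching exclusion line. Carry the same item into the eligibility CRF, if it is not already there, and have it completed before randomisation. Because allocation is tied to enrolment, the question belongs in the screening described in Section 7.1 and should not be left to device placement. It would also help to state whether the tincture is used on the sham device, so that it is clear whether both arms carry the risk.

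The cost is one line in 6.3, one checkbox and the protocol amendment that carries them. A few candidates may become ineligible, all of them people for whom Section 2.3 already contraindicates the device. No endpoint, sample size or analysis changes.

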3 STUDY OBJECTIVES

The aim of this research is to gather data regarding the feasibility of the Bridge system for the management of pain following total hip arthroplasty (THA; a.k.a. total hip replacement).

4 STUDY DESIGN

[figure not shown]
[figure not shown]
This is a prospective, randomized, blinded, sham-controlled study design in up to 60 subjects. Individuals scheduled for primary total hip arthroplasty will be approached and consented for the trial. Patients undergoing primary unilateral total

hip surgery will be expected to be discharged on the day of surgery, or the next day but no later than 48 hrs following surgery. The anticipated duration of subject participation in this study will be approximately 1 month.

